9.2 Expected accrual rate, accrual duration, and study duration

Our anticipated accrual rate is 6-8 patients per month. Thus, it should take approximately 3-5 months to accrue the 29 patients needed for the trial. Allowing for 6 months of follow-up to obtain the primary endpoint on the last patient enrolled and 3 months to assemble, analyze and interpret the data the total study duration is projected to be at most 2 years.

9.3 Analysis of AE data

Analysis of AE data will primarily be descriptive based on MedDRA coding of events. The proportion of subjects experiencing an SAE and the proportion experiencing a Grade 3 or higher will be recorded. AE will be compared to published data.

9.4 Analysis of anti-SARS-CoV-2 titers

Analysis of titers will be descriptive, comparing the geometric mean titers at days at 0, 7, 14, and 28 days.

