2. Age \geq 18 years of age
3. No receipt of convalescent plasma

Immunologic Controls:

1. PBMCs with 5-10 million cryopreserved cells per specimen present in the prospective COVID 19 Biorepository
2. Serum or plasma 500 UI each from up to 50 patients present in the COVID-19 Biorepository

Assessment and Data Acquisition:

1. Baseline: Age, sex, comorbidities, date of symptom onset, known COVID-19 contact, type of admission to the floor or ICU, APACHE score (ICU scoring system to classify disease severity and mortality risk), SOFA score (mortality prediction score based on organ function), clinical status, vital signs including temperature, respiratory rate, oxygen saturation, oxygen requirement, neutrophil count, lymphocyte count, CRP, chest x-ray, chest CT, location in hospital.
2. Safety and efficacy: Day 0 (baseline), 1, 2, 3, 4, 7, 14, 21, and 28 and once at day 60.
3. SARS-CoV-2 PCR from OP or NP swabs: Day 0, 4, 7, 14 and at any time when there is clinical suspicion for COVID-19.
4. Outcome measures: increased O₂ requirement (PaO₂/FiO₂ ratio or SpO₂/FIo₂), supplemental oxygen strategy (nasal cannula, high flow nasal cannula, noninvasive ventilation, intubation and invasive mechanical ventilation, rescue ventilation i.e. neuromuscular blocking agents, prone positioning, corticosteroids, ECMO), vasopressors, renal support, ICU LOS, ICU mortality, hospital LOS, hospital mortality, 28 day mortality.
5. Serum or plasma antibody titer² to SARS-CoV-2: Day 0, 7, 14, and 28. Samples from the COVID-19 Biorepository from non-transfused patients will be assayed at two similar timepoints as Immunologic Controls.
6. Blood for immune evaluations of cellular and humoral immunity before CIP infusion (day 0) and 7, 14 and 28 days after CIP infusion. Immune testing may be done at any time if the PI determines there is a need to evaluate acute immune responses (cytokines/chemokines levels). Samples from the Prospective COVID-19 Biorepository from non-transfused patients will be assayed at two similar timepoints as Immunologic Controls.
7. "Clinical controls" will have all relevant datapoints collected via chart review (i.e. biospecimens will not be collected prospectively)

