2.2 Secondary Objectives

- Evaluate safety of CIP
- Evaluate cellular and humoral responses before CIP treatment and at CIP treatment.
- Evaluate the effect of CIP as compared to non-transfused immunologic control patients.

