2.3 Study Design

This is a single arm phase II trial to assess preliminary efficacy and confirm safety of infusions of anti-SARS-CoV-2 convalescent plasma in hospitalized patients with acute respiratory symptoms **with or without** confirmed interstitial COVID-19 pneumonia by CXR or chest CT. A total of 29 eligible subjects will be enrolled to receive high titer anti-SARS-CoV-2 plasma. Participants will be compared to a historical control group via retrospective chart review.

In addition, the following Immunologic Controls will be used to meet secondary objectives described above:

1. PBMCs with 5-10 million cryopreserved cells per specimen will be obtained from the prospective COVID 19 Biorepository (2 timepoints per patient t (60 specimens total) and assessed for cellular and humoral immune responses.
2. Serum or plasma 500 UI each from up to 50 patients in the Covid-19 Biorepository will be collected (2 timepoints from each patient) (100 total specimens) will be evaluated for antibody and cytokine responses.

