5.2.7 Enrollment, Screen Failures, and Study Completion

Patients are considered enrolled from time consented to participate until designated as a screen failure or have either been discontinued from the study or completed it. A screen failure is a patient who signed informed consent, but then was determined to be ineligible or withdraws from the study. Subjects are considered to have completed the study when they are followed through day 60 or have had an adverse event or death occurred prior to day 60.

Day -1 to 0 Baseline:

- A. Subject informed consent (obtained before performing study related activities)
- B. Baseline Evaluation at screening.
 1. Demographics (Age, sex ethnicity, race)
 2. Medical history (timing of exposure to COVID-19 source patient, acute and chronic medical condition, medications, allergies.) Any medical condition arising after consent should be recorded as AE.
 3. COVID-19 symptom screen (fevers, cough, shortness of breath, diarrhea, anosmia), onset of symptoms, source of contagion
 4. Vital signs

5. COVID-19 testing (RT-PCR) from nasopharyngeal, throat, tracheal aspirate or bronchoalveolar lavage and stool (optional) samples
6. Blood typing, CBC with differential, comprehensive metabolic panel
7. Serological testing: anti-SARS CoV-2 titers
8. Immune testing samples
9. Urine or serum pregnancy test for females of childbearing potential. Results from laboratory tests obtained up to 7 days before enrollment may be used for the pregnancy test.
10. Determination of eligibility as per inclusion/exclusion criteria, age, consent, positive for COVID-19, respiratory symptoms within 72 hours of admission

DAY 0 Baseline and Infusion:

1. Study Plasma Administration: 1-2 units of plasma will be transfused over 1-2 days. Time at start and end of infusion will be recorded and vital signs will be measured immediately prior to infusion, 10-20 minutes after start of infusion, at completion of infusion and 30-60 minutes after the end of the infusion
2. COVID-19 symptom screen (fevers, cough, shortness of breath)
3. Assessment of clinical status (8-point ordinal scale)
4. New medical conditions, concomitant medication, AE evaluation
5. Physical examination
6. COVID-19 testing (RT-PCR) from nasopharyngeal, throat or stool (optional) samples
7. Blood typing, CBC with differential, comprehensive metabolic panel, C-reactive protein
8. Serological testing: anti-SARS CoV-2 titers

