9.0 STATISTICAL CONSIDERATIONS

9.1 Power calculation

Twenty-nine evaluable patients will have 80% power to declare a significant decrease in ICU admissions from a historical control of 50% of hospitalized patients to 25% with a two-sided type I error of 0.05 (reject ICU admission rate=50% if only 8 or less patients are admitted to ICU among 29 evaluable patients).

Data analysis: For categorical clinical endpoints, frequency with percentage will be summarized. For the quantitative clinical variables and immune response variables measured in this objective, we will produce summary statistics (including means, medians, and standard deviations) for data at pre- and post-CIP infusions. Subsequent analyses will compare the serologic and neutralization antibody titers for anti-SARS-COV-2 antibodies and immune response variables (after a suitable data transformation to improve normal distribution, if necessary) pre- and post-treatment using a paired t-test (or Wilcoxon sign ranked test if the data are not approximately normally distributed). The level of each measured immune biomarker measured at the follow-up time points will be plotted to visually show the change of immune responses over time. To explore whether immune responses at pre- or peak improvement at post-CIP infusions associate with clinical endpoints (such as ICU admission, intubation), logistic regression for binary endpoints and Cox regression for time to event endpoints will be used to analyze each measured immune biomarker respectively. These effects will be compared to biospecimen from non-transfused immunologic controls. Analyses will adjust for other covariates such as age and co-morbidities. No

multiplicity adjustment is planned due to the nature of being exploratory. A two-sided p-value of < 0.05 will be considered significant.

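### The recipient-versus-control immune comparison in Section 9.1 should name days since symptom onset as a covariate, because controls have no infusion day to align on

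*Combined protocol and SAP*

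**What the plan says.** The third secondary objective (Section 2.2) is: "Evaluate the effect of CIP as compared to non-transfused immunologic control patients". Section 2.3 supplies the material: "Serum or plasma 500 UI each from up to 50 patients in the Covid-19 Biorepository will be collected", at two timepoints per patient, for antibody and cytokine responses.

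The analysis text is short. Section 9.1 says "These effects will be compared to biospecimen from non-transfused immunologic controls" and then "Analyses will adjust for other covariates such as age and co-morbidities". Section 9.4 adds "Analysis of titers will be descriptive, comparing the geometric mean titers at days at 0, 7, 14, and 28 days"; it describes recipients and does not mention controls.

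On timing, Section 1.0 (Assessment and Data Acquisition) says "Samples from the COVID-19 Biorepository from non-transfused patients will be assayed at two similar timepoints as Immunologic Controls". It does not say which two recipient visits are meant, what the days are counted from, or what window applies. The immunologic-control criteria at the end of Section 4.5 set no condition on illness timing.

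Symptom onset is recorded for recipients: Section 1.0 lists "Baseline: Age, sex, comorbidities, date of symptom onset, known COVID-19 contact", and the screening visit in Section 5.2.7 includes "onset of symptoms, source of contagion". No stated analysis uses it.

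**The concern.** Recipient samples are dated from infusion. Controls have no infusion, so their samples must be dated from something else, and the plan does not say what. Antibody titers change with time since symptom onset, whether or not plasma is given. If control samples come earlier or later in illness than recipient samples, an analysis using only the named covariates attributes part of that timing difference to plasma.

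This comparison carries the plan's immunologic questions. Section 1.0 asks whether plasma enhances the patient's own anti-COVID-19 response, and Section 5.6.2 raises the opposite possibility, an attenuated response. Recipient pre/post data alone cannot separate either from natural seroconversion, so the answer depends on the controls.

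**Working it through.** The plan gives no figure for this comparison. Its only sample-size calculation concerns ICU admission and enters here only as the number of recipients.

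**Inputs from the documents.** 29 recipients (Section 9.1); up to 50 serum or plasma controls with two samples each (Section 2.3).

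**Assumed inputs; none is in the documents.** With t = days since onset, log10 titer = log10(2) × min(t, Tp)/Td + patient effect (SD 0.4) + assay error (SD 0.3). Doubling time Td is 2, 4 or 7 days. The plateau Tp is day 14, day 21 or none. The first sample is at mean day 7 in recipients (SD 3, minimum 1) and later by the gap in controls. The second sample follows 7 or 14 days after the first in both groups. There is no plasma effect, so the true ratio is 1.00.

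**Step 1: one timepoint, rising phase, no adjustment.** The ratio is off by 2^(gap/Td).
- 1-day gap: 2^(1/2), 2^(1/4), 2^(1/7) = 1.41, 1.19, 1.10.
- 3-day gap: 2^(3/2), 2^(3/4), 2^(3/7) = 2.83, 1.68, 1.35.

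**Step 2: adjusting for the first log titer.** This can be approximated by hand. Let a = log10(2)/Td. The variance of the first log titer within a group is about 9a² + 0.16 + 0.09. For Td = 2, a = 0.1505 and the variance is 0.2039 + 0.16 + 0.09 = 0.4539.
- Steady rise: the slope on the first titer is (0.2039 + 0.16)/0.4539 = 0.802. The leftover log10 bias is −(1 − 0.802) × gap × a. A 1-day gap gives −0.030, ratio 0.93. A 3-day gap gives −0.089, ratio 0.81.
- Second sample on the plateau: the slope is 0.16/0.4539 = 0.353. The bias is +0.353 × gap × a. A 1-day gap gives +0.053, ratio 1.13. A 3-day gap gives +0.159, ratio 1.44.

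So first-titer adjustment alone leaves a bias whose direction depends on the unknown titer course.

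**Step 3: simulation over all combinations, controls later in illness.** Range of the mean estimated ratio:

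| Analysis | 1-day gap | 3-day gap |
|---|---|---|
| Second sample only | 0.72 to 1.00 | 0.35 to 0.99 |
| Change versus change | 0.99 to 1.38 | 1.00 to 2.70 |
| Adjusted for first titer | 0.93 to 1.12 | 0.81 to 1.44 |

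Change versus change is unbiased (1.00) if the rise is steady and the intervals are equal, but not once titers plateau. With controls 3 days earlier, first-titer adjustment gives 0.69 to 1.23.

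**Step 4: adding days since onset at the first sample.** With a 3-day gap the range becomes 0.97 to 1.01. If onset dates carry a recording error of SD 2 days, it is 0.90 to 1.18.

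**Step 5: precision.** The 95% half-width factor is about 1.5 with or without the onset term when there is no gap, and about 1.6 with it at a 3-day gap (1.74 with 25 controls in one setting: Td 4, Tp 14, interval 7 days). The extra covariate costs almost nothing.

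**The case against.** The case for leaving the plan alone has real parts.

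- **Section 9.4 is not wrong.** It is a descriptive recipient summary, and a reader might infer that it is a faulty between-group analysis. The text does not support that, since it mentions no controls. The point belongs to Section 9.1.
- **The contrast is not specified.** In Section 9.1 the control sentence follows the logistic and Cox models relating biomarkers to clinical endpoints, and may attach to those. No titer ratio is written down. This stands: the plan leaves the comparison open, and it would be too strong to say it has chosen a biased one. But the objective and the control specimens still require a comparison.
- **Timing is partly handled.** Two similar timepoints are promised, both groups are hospitalized (Section 8.3), and the covariate list is open. The repository protocol, which is not part of these documents, may set a schedule. These reduce the risk, but none commits to a common time scale.
- **Control onset dates may already be available.** The title of Section 4.3 says its chart-review control group covers control specimens, and Section 1.0 says clinical controls have their relevant data abstracted from charts. Section 4.5 lists immunologic controls separately, so coverage is ambiguous. A reader should not infer that the dates are unobtainable.
- **Recipients' symptom timing may be limited.** Sections 4.1, 5.1 and 5.2.7 can be read as tying symptoms to within 72 hours of admission. Section 1.0 favours an enrollment window. Neither reading sets a limit for controls.
- **The large figures are extremes.** Ratios of 0.35 or 2.70 need a 3-day gap with a 2-day doubling time, and an analysis without first-titer adjustment. With that adjustment, a 1-day gap gives a bias well inside the CI width, and even the 3-day range with controls later stays inside a factor of about 1.6.

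**Conclusion.** The point holds as a cheap improvement to a secondary, exploratory comparison. Section 9.1 commits to comparing recipients with controls who have no infusion day, Section 1.0 gives their samples no time origin, and the variable that would put both groups on one scale is collected for recipients but not named in any analysis.

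The size is unknown. Under the assumptions above, with first-titer adjustment and controls later in illness, the expected ratio under no effect is 0.93 to 1.12 for a 1-day gap and about 0.8 to 1.45 for a 3-day gap.

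A reader might infer that the groups do differ in illness timing, or that the titer result will be wrong. The documents give no onset distribution for either group, so they support only a conditional statement. The primary endpoints and stopping rules are untouched.

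**What to change.** In Section 9.1:

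1. Record the date of symptom onset for immunologic controls by chart review, the method Sections 1.0 and 4.3 already use for controls. This assumes specimens can be linked to charts.
2. Add days since symptom onset at the first sample to the named covariates, alongside first log titer (the day-0 baseline sample for recipients), age and co-morbidities.
3. Report the recipient-to-control ratio of geometric mean titers with a 95% CI.
4. State that post-infusion recipient titers include donor antibody, so the ratio is a total effect and not evidence of an enhanced own response.
5. Use the control pairs available and account for the interval between samples in the model. Do not restrict pairs to a fixed window such as 14 ± 3 days: among hospitalized patients that could select those with long stays.

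The cost is a few lines of text and one date abstracted for up to 50 patients, with no new samples or assays. Onset dates are self-reported, so some timing bias may remain, and the comparison stays non-randomized and exploratory.

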10.0 REGISTRATION AND REQUIRED DATA

10.1 Pre-Study

All patients on-study will be evaluated prior to initiation of therapy. Baseline studies will be completed prior to on-study.

10.2 Protocol Registration

Subject must meet all eligibility requirements listed in Section 4.0 prior to enrollment. Subjects who are consented to the study must be registered in the Clinical Trials Office. All subjects who have signed an informed consent should have demographics and date of signed informed consent entered into the database.

10.3 Evaluations and Assessments

All evaluations and assessments should be completed as described in Table 1. Any assessments not described in detail below should be done according to standard of care practices.

10.4 Medical History/Physical Examination

A complete medical history and physical examination will be obtained at the Pre-Study Assessment. The medical history includes clinically significant diseases, surgeries, history of cancer (including date of diagnosis, location of disease, prior cancer therapies and procedures), and all medications (e.g., prescription drugs, over-the-counter drugs, herbal/homeopathic remedies, nutritional supplements). A physical examination documented by the primary physician in the hospital chart will be performed at the re-Study Assessment and prior to the CIP infusion for baseline conditions) only. Physical examinations will include the following body systems: general appearance (including height and body weight), skin, neck, HEENT (head, ears, eyes, nose and throat), heart (auscultation of heart sounds), lungs (auscultation of lung fields), abdomen palpation and auscultation of bowel sounds, lymph nodes, extremities, and nervous system.

10.5 Vital Signs

Vital signs including respiratory rate, pulse rate, systolic blood pressure [SBP], and diastolic blood pressure [DBP] and body temperature, and supplemental oxygen requirements, will be collected at Pre Study Assessment.

10.6 Laboratory Parameters

Blood samples for clinical labs will be obtained as described in the Time and Events table for

adverse event determination and clinical decision making.

10.7 Laboratory and Clinical Data Review

The Investigator, or designee, must review all laboratory values and report any clinically significant change compared to the baseline sample as an AE. When reporting such AEs the Investigator will use the appropriate clinical term, rather than the laboratory test result (e.g. anemia versus low hemoglobin).

10.8 Immune Evaluations

Immune evaluations (IEs) will be conducted as delineated in Table 1. Baseline serum and cells will be aliquoted from the pheresis. Blood draws (4 green top tubes containing approximately 50 mL of anti-coagulated blood and 1 red top tube containing 8 mL of serum) will be collected at designated time points at 0, 7, 14, and 28 days after CIP infusion. All patients receiving any dose of study treatment should be assessed for immune markers. Evaluations will include:

- Serum cytokine/chemokine levels
- Phenotyping of T cells and T cell subpopulations, TCR repertoire analysis, monocyte, B cells, and NK cell by flow cytometry.
- Cytotoxic activity and IFN γ production in PBMC populations. An immune response will be defined as a 30 IFN γ Elispots per million cells plated above the background of unstimulated spontaneous IFN γ Elispots per million cells plated.
- Additional assays may be performed on available samples to evaluate Th₁/Th₂ responses in single cell RNA sequencing on selected samples.

10.9 Subject Status Definitions

- Enrolled: All subjects who sign an informed consent will be considered enrolled on the study. All subjects consented on the study must be entered into Clinical Trials Office Database.
- Screen Failure: A subject who is withdrawn or discontinues from study screening prior to being on study is considered a screen failure. Screen failures are not considered a study accrual and will be replaced. Note: The IRB defines any individual that has signed an informed consent as an enrollment in this study and so screen failures should be reported to the IRB with enrollment numbers.
- On-Study: A subject is considered on-study on the date when the study team has confirmed the subject has met all of the inclusion and none of the exclusion criteria, and the treating physician/surgeon or study PI has signed off on the confirmation.
- On-Treatment: A subject is considered on-treatment on the date that they receive the first study treatment. A subject who is withdrawn or discontinues from the study after receiving at least 1 infusion is considered a discontinuation and will not be replaced.
- On Follow-up: A subject is considered on follow-up on the date that they have met any of the criteria in section 4.0.
- Off-Study: A subject is considered off-study if they are removed from the study for any of the reasons listed in section 4.0 or if they have completed all study assessments through follow-up.
- Immunologic Controls: A subject for whom biospecimen is obtained from the COVID-19 Biorepository.

11.0 RISKS AND BENEFITS

11.1 Potential Benefits of Treatment for the Patient

The benefits of antiviral therapy with anti-COVID-19 plasma in patients with respiratory symptoms consistent with interstitial pneumonia at high risk for requiring ICU admission are not known. It is anticipated that treatment will decrease the risk of disease progression, decrease ICU admissions, and decrease aggressive respiratory support including possible mechanical ventilation and other ICU support.

11.2 Risks of Plasmapheresis for the Donor

There is small risk of breach of privacy and/or confidentiality. The most common risk of blood draw and plasmapheresis is pain. Other risks include tingling of the lips and fingers, bruising at the IV site(s), mild tightness in the chest, a cough, low and/or high blood pressure, a slow pulse rate, and fainting or passing out (not often). There is a rare risk of allergic reactions such as rash, hives, shortness of breath or shock and infection. The risks of citrate include muscle cramps, numbness, cold feeling, tingling sensations in the lips and fingers, feeling anxious, and seizures with abnormal heart rhythms, and allergic reaction including death being rare.

